2.1 RATIONALE FOR DOSE SELECTION

A. Radiation Therapy: All patients in this trial will be treated with fractionated Stereotactic body radiation therapy. Treatment of oligometastatic lung cancer in this fashion has been explored in multiple studies with encouraging long term survival data (37-39). In a recent multi-institutional randomized trial from MD Anderson cancer center, patients with oligometastatic lung cancer where randomized to systemic therapy plus SBRT to all metastatic sites versus systemic therapy alone (40). The study was terminated early after a planned interim safety analysis showed significantly improved in progression free survival in the SBRT group (11.9 vs 3.9 months) at median follow up of 12 months. Patients in the SBRT group were less likely to develop new lesions compared to patients on systemic therapy alone suggesting SBRT acted similarly to systemic therapy.

In a series of mouse tumor models treated with an anti-CTLA-4 antibody combined with 3 different radiation regimens, enhanced tumor responses were observed when treated with fractionated radiation regimens of $8 \text{ Gy} \times 3$ or $6 \text{ Gy} \times 5$ administered on consecutive days, but not with $20 \text{ Gy} \times 1$ (19). The fractionated regimens, but not the single radiation dose, also resulted in abscopal effects. For uniformity, we will adhere to the radiation dose guidelines as prescribed in the NRG-BR001 protocol examining the role of SBRT for oligo-metastatic disease (41). Dose reductions are allowed to pre-specified doses at the treating physician's discretion if dosimetric criteria are not achievable. Dose schedules and prescriptions are described under radiation treatment.

B. Immunotherapy: All patients in this trial will be treated with either Nivolumab or Pembrolizumab at FDA approved dosing and indications (1, 36). If new FDA approved anti-PD-1 therapies emerge during the study duration, the study will be modified with IRB approval to allow addition of newly approved therapies to the protocol. (36). These FDA approved dosing schedules are established and have a favorable toxicity profile and will allow direct comparison of outcomes to immunotherapy alone trials vs immunotherapy plus SBRT.

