7. IMMUNOTHERAPY

Immunotherapy administration will commence or continue following the conclusion of SBRT/SABR.

Immunotherapy will be administered as an IV infusion as specified. It is not to be administered as an IV push or bolus injection. At the end of the infusion the administration line will be flushed with a sufficient quantity of normal saline per standard of care. Infusions will continue on a standard schedule for the specific immunotherapy agent with pre-treatment assessments for adverse effects using a standard questionnaire.

Immunotherapy administration will be delayed in the case of any of the following:

Any Grade ≥ 2 non-skin, drug-related adverse event, with the following exceptions:— Grade 2 drug-related fatigue or laboratory abnormalities do not require a treatment delay

Any Grade 3 skin, drug-related adverse event

Any Grade 3 drug-related laboratory abnormality, with the following exceptions for lymphopenia, leukopenia, AST, ALT, or total bilirubin:

- Grade 3 lymphopenia or leukopenia does not require dose delay
- If a subject has a baseline AST, ALT or total bilirubin that is within normal limits, delay dosing for drug-related Grade ≥ 2 toxicity
- If a subject has baseline AST, ALT, or total bilirubin within the Grade 1 toxicity range, delay dosing for drug-related Grade ≥ 3 toxicity

Any adverse event, laboratory abnormality, or intercurrent illness which, in the judgment of the investigator, warrants delaying immunotherapy administration.

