
• Enterocolitis hemorrhagic
 
 • Gastrointestinal (GI) perforation • Necrotizing colitis 
Diarrhea: Patients who experience diarrhea should be advised to drink liberal quantities of clear fluids. If sufficient oral fluid intake is not feasible, fluid and electrolytes should be substituted via IV infusion.
	
Grade 2
	
Hold until ≤Grade 1. Resume at same dose level. May increase dosing interval by 1 week if it takes more than 4 weeks for toxicities to resolve.
	
GI consultation and endoscopy is recommended to confirm or rule out colitis for grade 2 diarrhea that persists >1 week or grade 1-2 diarrhea with rectal bleeding (additional guidelines for the treatment of persistent colitis are provided below). Grade 2 diarrhea should be treated with the addition of oral diphenoxylate hydrochloride and atropine sulfate four times daily and budesonide 9 mg daily. Grade 2 diarrhea with diffuse ulceration and bleeding seen on endoscopy may require oral steroids with prolonged taper and represent an increased risk for the development of bowel perforation. Consider prophylactic antibiotics for opportunistic infections. When symptoms improve to Grade 1 or less, steroid taper should be started and continued over no less than 4 weeks. • In patients with Grade 2 enterocolitis, IMMUNOTHERAPY should be withheld and anti-diarrheal treatment should be started. If symptoms are persistent for more than one week, systemic corticosteroids should be initiated (eg, 0.5 mg/kg/day of prednisone or equivalent). When symptoms improve to Grade 1 or less, corticosteroid taper should be started and continued over at least 1 month.
	
 • Blood and/or mucus in stool with or without fever • Constipation • Diarrhea • Ileus • Nausea and/or vomiting • Peritoneal signs consistent with bowel perforation • Rectal bleeding • With or without fever 
Patients with diarrhea should be
	
or parasitic infection, viral gastroenteritis, or the first manifestation of an inflammatory bowel disease by examination for stool leukocytes, stool cultures, and a Clostridium difficile titer.

Event(s)	CTCAE v4.03 Grade	Management	Action/Supportive Care Guidelines

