Colitis events (continued)	Grade 3–4	
Withhold IMMUNOTHERAPY
 
Discontinue if unable to reduce corticosteroid dose to < 10 mg per day prednisone equivalent within 12 weeks of toxicity
	
 • In patients with Grade 3 enterocolitis, OPDIVO will be permanently discontinued and treatment with systemic corticosteroids should be initiated at a dose of 1–2 mg/kg/day of prednisone or equivalent. When symptoms improve to Grade 1 or less, corticosteroid taper should be started and continued over at least 1 month. Consider prophylactic antibiotics for opportunistic infections. 
For Grade 3–4 diarrhea (or Grade 2 diarrhea that persists after initial steroid treatment),
 
 • Rule out bowel perforation. Imaging with plain films or computed tomography (CT) can be useful. • Consider consultation with gastroenterologist and confirmation biopsy with endoscopy. • Treat with intravenous (IV) steroids (methylprednisolone 125 mg) followed by high-dose oral steroids (prednisone 1–2 mg/kg once per day or dexamethasone 4 mg every 4 hours). When symptoms improve to Grade 1 or less, steroid taper should be started and continued over no less than 4 weeks. Taper over 6–8 weeks in patients with diffuse and severe ulceration and/or bleeding. • If IV steroids followed by high-dose oral steroids does not reduce initial symptoms within 48–72 hours, consider treatment with infliximab at 5 mg/kg once every 2 weeks. Discontinue infliximab upon symptom relief and initiate a prolonged steroid taper over 45–60 days. If symptoms worsen during steroid reduction, initiate a tapering of steroids starting at a higher dose of 80 or 100 mg followed by a more prolonged taper and administer infliximab. CAUTION: infliximab is contraindicated in patients with bowel perforation or sepsis^b. • If symptoms persist despite the above treatment a surgical consult should be obtained.

Event(s)	CTCAE v4.03 Grade	Management	Action/Supportive Care Guidelines	Symptoms ^a	Differential Diagnosis

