Eye event: Uveitis (iritis, iridocyclitis)	Grade 1	Discontinue IMMUNOTHERAPY if symptoms persist despite treatment with topical immunosuppressive therapy	
 • Evaluation by an ophthalmologist is strongly recommended. • Treat with topical steroids such as 1% prednisolone acetate suspension and iridocyclitics. 	Symptoms may include (but are not limited to): 
 • Blurred vision • Diffuse erythema and a prominent blush on the sclerae • Dryness of the eyes • Pain • Photophobia 	All attempts should be made to rule out other causes such as metastatic disease, infection, or other ocular disease (e.g., glaucoma or cataracts).
	Grade 2	Discontinue IMMUNOTHERAPY if symptoms persist despite treatment with topical immunosuppressive therapy and do not improve to Grade 1 within the retreatment period OR requires systemic treatment.	
 • Evaluation by an ophthalmologist is strongly recommended. • Treat with topical steroids such as 1% prednisolone acetate suspension and iridocyclitics. 		
	Grade 3-4	Discontinue IMMUNOTHERAPY.	
 • Treat with systemic corticosteroids such as prednisone at a dose of 1-2 mg/kg per day. When symptoms improve to \leq Grade 1, steroid taper should be started and continued over no less than 4 weeks. 		

Event(s)	CTCAE v4.03 Grade	Management	Action/Supportive Care Guidelines	Symptoms ^a	Differential Diagnosis
Hepatic events 
 Hepatitis Hepatitis, Autoimmune 	Grade 1-2	Withhold IMMUNOTHERAPY if there is a treatment-emergent concurrent elevation of ALT and bilirubin that corresponds to an upward shift of 2 or more grades in both parameters.	
 Monitor liver function tests more frequently until returned to baseline values. 	Symptoms may include (but are not limited to): 
 Elevations in: 
 AST >2.5 ULN ALT >2.5 ULN Total bilirubin >1.5 × ULN 	All attempts should be made to rule out other causes such as metastatic disease, progressive liver disease, viral hepatitis,

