Skin events 
 • Dermatitis • exfoliative Erythema • multiforme Stevens-Johnson syndrome Toxic epidermal necrolysis 	Grade 1-2	No change in dose	Symptomatic treatment should be given such as topical glucocorticosteroids (eg, betamethasone 0.1% cream or hydrocortisone 1%) or urea-containing creams in combination with oral antipruritics (eg, diphenhydramine HCl or hydroxyzine HCl). Treatment with oral steroids is at investigator discretion for Grade 2 events.	All attempts should be made to rule out other causes such as metastatic disease, infection, or allergic dermatitis.
	Grade 3	Hold IMMUNOTHERAPY.	Consider dermatology consultation and biopsy for confirmation of diagnosis. 
 • Treatment with oral steroids is recommended, starting with 1 mg/kg prednisone or equivalent once per day or dexamethasone 4 mg four times orally daily. When symptoms improve to Grade 1 or less, steroid taper should be started and continued over no less than 4 weeks. 	
	Grade 4	Permanently discontinue IMMUNOTHERAPY.	Dermatology consultation and consideration of biopsy and clinical dermatology photograph. Initiate steroids at 1-2 mg/kg prednisone or equivalent. When symptoms improve to grade 1 or less, steroid taper should be started and continued over no less than 4 weeks.	
If considered to be immune related, ≥ Grade 3 or result in dose modification or discontinuation: 
 • Pruritus • Rash • Rash generalized • Rash maculo-papular • Vitiligo 	≤ Grade 1	No change in dose		
	Grade 2	No change in dose		
	Grade 3	No change in dose	Grade 3 drug-related thrombocytopenia >7 days or associated with bleeding requires discontinuation.	
	Grade 4	Hold IMMUNOTHERAPY until resolves to ≤ Grade 1. May increase the dosing interval by 1 week.	Grade 4 drug-related thrombocytopenia >7 days or associated with bleeding requires discontinuation.	
Thrombocytopenia				

^a The signs and symptoms may be associated with any of the diagnoses in the associated "Event(s)" column.

^b REMICADE (Infliximab) prescribing information

^c If symptoms indicate possible new or worsening cardiac abnormalities, additional testing and/or a cardiology consultation should be considered.

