Since the development of this study, additional data regarding immunotherapy has emerged. Additional immunotherapy agents have shown efficacy in the treatment of metastatic NSCLC in the first line setting. Pembrolizumab is a humanized monoclonal antibody against the PD-1 with antitumor activity in advanced NSCLC expressing PD-L1. The Keynote-024 trial compared previously untreated advanced NSCLC with PD-L1 expression on at least 50% of tumor cells and no sensitizing mutation of the epidermal growth factor receptor gene or translocation of the anaplastic lymphoma kinase gene to receive either Pembrolizumab (at a fixed dose of 200 mg every 3 weeks) or the investigator's choice of platinum-based chemotherapy (1). Median progression free survival, 6 month overall survival and response rate were significantly improved in the Pembrolizumab arm. Pembrolizumab has now redefined initial systemic therapy for PD-L1 expressing tumors in the metastatic setting.

We hereby propose that immunotherapy in this trial now include Nivolumab or Pembrolizumab as long as patients are eligible.

References

1. Reck M et al. *N Engl J Med.* 2016 Nov 10;375(19):1823-1833. Epub 2016 Oct 8.

STUDY ADDENDUM 2.

Since the last re-authorization of the study, there have been several changes in the immunotherapy landscape from randomized phase III trials. These changes affect our proposed utilization of stereotactic body radiation therapy (SBRT) and immunotherapy in 17-009.

First line systemic therapy for metastatic lung adenocarcinoma now includes combination chemotherapy and immunotherapy. Keynote-189 showed an improved overall survival with pembrolizumab/alimta and carboplatin vs carboplatin/alimta alone (1). This survival benefit was higher with increasing PD-L1 expression but was maintained regardless of PD-L1 expression. Similarly, Key-407 showed an improved overall survival in patients with metastatic squamous cell lung carcinoma with combination carboplatin/taxol/pembrolizumab vs carboplatin/taxol alone (2) with PD-L1 expression $\geq 1\%$. Additionally, the PACIFIC trial showed an significant increase in overall survival in patients with stage III non-small cell carcinoma when Darvalumab was added following concurrent chemoradiation vs observation (3).

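### Appendix I gives two incompatible rules for Grade 3 enterocolitis on nivolumab, and its permanent-stop sentence names only one brand and one grade

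*Protocol*

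**What the plan says.** Appendix I sets dose-modification and supportive-care guidance by event and grade. In the Grade 3-4 row for colitis events, the Management cell tells the investigator to withhold immunotherapy and then sets a condition for stopping: "Discontinue if unable to reduce corticosteroid dose to < 10 mg per day prednisone equivalent within 12 weeks of toxicity". The Action/Supportive Care cell of that row opens with an instruction that carries no condition: "In patients with Grade 3 enterocolitis, OPDIVO will be permanently discontinued".

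The corresponding Grade 2 sentence uses an agent-neutral term: "In patients with Grade 2 enterocolitis, IMMUNOTHERAPY should be withheld". Its Management cell, which holds dosing until recovery to Grade 1 or less, agrees with it.

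Nivolumab is not the only agent allowed. Section 2.1, part B, says: "All patients in this trial will be treated with either Nivolumab or Pembrolizumab". Study Addendum 1 says: "We hereby propose that immunotherapy in this trial now include Nivolumab or Pembrolizumab as long as patients are eligible". Section 4.3 is wider still and refers to approved agents against PD-1 or PD-L1.

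**The concern.** Both cells stop dosing at once, so the immediate response to severe colitis is not in doubt. They part company later, when the colitis has settled and steroids have been tapered. One cell then triggers no stop; the other has already ended treatment for good. Whether to expose a patient again to a PD-1 agent after severe bowel toxicity is a safety decision, and two investigators following the same row could decide it differently for similar patients.

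The scope of the permanent-stop sentence adds a second difficulty. It names OPDIVO, the brand of nivolumab, and Grade 3. Taken at its word, it says nothing about pembrolizumab and nothing about Grade 4, so the more severe grade would carry the milder rule.

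**Working it through.** No arithmetic applies. The check sets the two cells of the Grade 3-4 colitis row against each other for the cases that can arise, and then looks for any other provision that would decide between them.

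**Does the row cover enterocolitis?** Yes. Hemorrhagic enterocolitis is among the listed colitis events, and the Action cell itself speaks of enterocolitis. Both cells therefore apply.

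**The cells side by side**

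| Case | Management cell | Action cell | Result |
|---|---|---|---|
| Grade 3 enterocolitis, nivolumab, steroids below 10 mg/day within 12 weeks | Withhold; stop not triggered | Permanent stop | Contradiction |
| Grade 3 enterocolitis, nivolumab, taper fails | Withhold, then discontinue | Permanent stop | Same outcome |
| Grade 3 enterocolitis, pembrolizumab | Withhold; conditional stop | Agent not named | Conditional rule alone |
| Grade 4 enterocolitis, either agent | Withhold; conditional stop | Grade not named | Conditional rule alone |

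The contradiction is thus confined to nivolumab patients at Grade 3 whose taper succeeds. The gap in scope concerns the last two lines.

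**Does anything else decide it?**

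- Section 7 introduces its list with "Immunotherapy administration will be delayed in the case of any of the following". It gives reasons for delay, including drug-related non-skin events of Grade 2 or higher, but no rule on permanent discontinuation after colitis.
- Section 4.3 defines dose-limiting toxicities that bear on continuing or stopping therapy. Grade 3 or higher non-hematologic toxicity counts, with exceptions for nausea, vomiting and diarrhea, and for Grade 3 immune-related effects that improve within 7-14 days on steroids. The window is 14 days from cycle 1, day 1, and the events must be at least possibly related to nivolumab. Later colitis, and colitis on pembrolizumab, fall outside it.
- Nothing in Appendix I says that the Action cell overrides the Management cell, or the reverse.

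**Could this be an extraction artefact or superseded text?** No. Both sentences are complete, stand in one intact row, and belong to the current appendix.

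**The case against.** **The specific sentence governs the general one.** On this reading the Action sentence is an exception to the row's general rule. The document does not say so, and the reading settles only Grade 3 on nivolumab. It would confirm that Grade 4 has the milder rule.

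**The appendix is guidance.** Its title does call the modifications recommended. That lowers the weight of the point, but the sentence itself is mandatory in form, and guidance that gives two answers in one row cannot be followed.

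**OPDIVO is leftover wording.** This is plausible, since the surrounding text speaks of immunotherapy and Addendum 1 brought in pembrolizumab. A treating oncologist is also unlikely to read a Grade 3 stop as licence for a milder rule at Grade 4. Both points make harm less likely. Neither removes the conflict between the two cells, and both favour correcting the word.

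**Section 4.3 is stricter at Grade 4.** Within its window, the exemption for steroid-responsive immune effects reaches only Grade 3. That stands, but it does not extend to later events.

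**A reader might infer that a taper condition is out of line with the rest of Appendix I.** The Grade 3-4 uveitis and pneumonitis rows say "Discontinue IMMUNOTHERAPY", and the Grade 4 skin row says "Permanently discontinue IMMUNOTHERAPY". The documents do not support the inference. The Grade 3-4 renal row has a similar steroid-taper condition and allows a restart; the Grade 3 skin row only holds; the severe endocrine and Grade 4 neutropenia rows hold as well. The appendix has no uniform pattern from which colitis departs.

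**A reader might also infer that the protocol permits rechallenge after Grade 4 colitis.** It does not say this. Where Appendix I allows dosing to resume, it says so, as for Grade 2 colitis, Grade 2 pneumonitis and renal events. The Grade 3-4 colitis row has no such instruction; the possibility only follows by implication from the conditional stop.

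**Conclusion.** The point holds in a narrow form. For Grade 3 enterocolitis on nivolumab, one row of Appendix I gives a conditional stop and an unconditional one, with no order of precedence. The unconditional sentence, read literally, leaves other agents and Grade 4 under the conditional rule alone.

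This should be corrected because it concerns re-exposure after severe toxicity. It does not threaten the trial's statistical conclusions: no sample size, error rate or endpoint changes, Section 5.4 asks patients who stop treatment to attend the remaining visits, and the pneumonitis rule of the pilot phase is untouched.

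No numerical size can be given. The protocol states no colitis frequency. One could cross agents with grades and count the cells lacking a clear stop, but that would count literal readings of one sentence, not patients affected, and Section 4.3 admits agents beyond the two named. The conclusion assumes only that both cells are meant to apply to the events listed in their row.

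**What to change.** Reword the Grade 3-4 colitis row so that the Management and Action cells state the same rule, replace OPDIVO with IMMUNOTHERAPY, and make Grade 4 no more lenient than Grade 3.

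The default that follows from the existing Action sentence is permanent discontinuation at Grade 3 and Grade 4. If resumption after Grade 3 is intended, say so in both cells, with the steroid threshold and the 12-week limit, and keep a permanent stop for Grade 4.

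Harmonise the Grade 3-4 renal row at the same time: its Management instruction is to discontinue, while its Action text sets a taper condition and allows a restart.

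The cost is wording in one appendix, with no change to visits, sample size or analysis. Under the stricter default, some patients whose colitis resolves would lose the option of re-treatment.

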APPENDIX II: DOSE LIMITS AND DVH CRITERIA

Table 3.0 OAR Dose Limits for 3 fraction SBRT

Serial Organ	Volume	Volume Dose (Gy)	Avoidance Endpoint
Spinal Cord	<0.03 cc	22.5	Myelitis
	<1.2 cc	13	Myelitis
Ipsilateral Brachial Plexus	< 0.03 cc	26	Brachial Plexopathy
	<3 cc	22	Brachial Plexopathy
Cauda Equina	<0.03 cc	25.5	Neuritis
	<5 cc	21.9	Neuritis
Sacral Plexus	<0.03 cc	24	Neuropathy
	<5 cc	22.5	Neuropathy
Trachea and Ipsilateral Bronchus*	<0.03 cc	30	Stenosis/Fistula
	<5cc	25.8	Stenosis/Fistula
Esophagus*	<0.03 cc	27	Stenosis/Fistula
	<5cc	17.7	Stenosis/Fistula
Heart/Pericardium	<0.03cc	30	Pericarditis
	<15 cc	24	Pericarditis
Great vessels*	<0.03cc	45	Aneurysm
	<10 cc	39	Aneurysm
Skin	<0.03cc	33	Ulceration
	<10cc	31	Ulceration
Stomach	<0.03cc	30	Ulceration/Fistula
	<10cc	22.5	Ulceration/Fistula
Duodenum*	<0.03cc	24	Ulceration

	<10cc	15	Ulceration
Bowel*	<0.03 cc	34.5	Ulceration
	<20cc	24	Colitis/Fistula
Rectum*	<0.03 cc	49.5	Ulceration
	<3.5 cc	45	Proctitis/Fistula
	< 20 cc	27.5	Proctitis/Fistula
Bladder	0.03cc	33	Cystitis/Fistula
	<15 cc	16.8	Cystitis/Fistula
Ureter	<0.03 cc	40	Stenosis
Penile bulb	< 3cc	25	Impotence
Femoral heads	<10 cc	24	Necrosis
Bile duct	< 0.03 cc	36	Stenosis
Renal hilum/vascular trunk	<15 cc	19.5	Malignant Hypertension
Rib	< 0.03 cc	50	Pain or Fracture
	< 5 cc	40	Pain or Fracture
Parallel Organ	Volume	Volume Dose (Gy)	Avoidance Endpoint
Lung (total)	<15% lung volume	20	Pneumonitis/Lung Function
	< 37% lung volume	11	Pneumonitis
	1500 cc	10.5	Basic Lung Function
	1000 cc	11.4	Pneumonitis
Ipsilateral kidney	<130 cc	12.3	Nephritis
Total Kidney	<200cc	15	Basic Renal Function
Liver	<700 cc	17.1	Liver function

*NOTE: Avoid circumferential irradiation.

Table 4.0 OAR Dose Limits for 5 fraction SBRT

Serial Organ	Volume	Volume Dose (Gy)	Avoidance Endpoint
Spinal Cord	<0.03 cc	28	Myelitis
	<0.35 cc	22	Myelitis
	<1.2 cc	15.6	Myelitis
Ipsilateral Brachial Plexus	< 0.03 cc	32	Brachial Plexopathy
	<3 cc	30	Brachial Plexopathy
Cauda Equina	<0.03 cc	32	Neuritis
	<5 cc	30	Neuritis
Sacral Plexus	<0.03 cc	32	Neuropathy
	<5 cc	30	Neuropathy
Trachea and Ipsilateral Bronchus*	<0.03cc	40	Stenosis/Fistula
	<5cc	32	Stenosis/Fistula
Esophagus*	<0.03cc	35	Stenosis/Fistula
	<5 cc	27.5	Stenosis/Fistula
Heart/Pericardium	<0.03 cc	38	Pericarditis
	<15 cc	32	Pericarditis
Great vessels*	<0.03 cc	53	Aneurysm
	<10 cc	47	Aneurysm
Skin	< 0.03cc	38.5	Ulceration
	< 10cc	36.5	Ulceration
Stomach	<0.5cc	35	Ulceration
	< 5cc	26.5	Ulceration
Duodenum*	< 0.5 cc	30	Ulceration

	< 5 cc	18.3	Ulceration
Bowel*	< 0.03 cc	40	Ulceration
	< 20 cc	28.5	Colitis/Fistula
Rectum*	< 0.03 cc	55	Ulceration
	< 3.5 cc	50	Proctitis/Fistula
	< 20 cc	32.5	Proctitis/Fistula
Bladder	< 0.03	38	Cystitis/Fistula
	< 15 cc	20	Cystitis/Fistula
Ureter	< 0.03 cc	45	Stenosis
Penile Bulb	< 3 cc	30	Impotence
Femoral head	< 10 cc	30	Necrosis
Bile Duct	< 0.03 cc	41	Stenosis
Renal hilum/Vascular Trunk	< 15 cc	23	Malignant Hypertension
Rib	< 0.03 cc	57	Pain or Fracture
	< 5 cc	45	Pain or Fracture
Parallel Organ	Volume	Volume Dose (Gy)	Avoidance Endpoint
Lung (total)	< 37% lung volume	13.5	Pneumonitis
	< 1500 cc	12.5	Basic Lung Function
	< 1000 cc	13.5	Pneumonitis
Total Kidney	< 200cc	18	Basic Renal Function
Liver	< 700 cc	21	Liver Function

*NOTE: Avoid circumferential irradiation.

